Primary Outcomes:	
Stage I:
 
 (a) Interest in different levels of risk disclosure feedback (b) Preferences for different levels of risk disclosure feedback (c) Perceived personal threat of DAT (d) Perceived benefits of/rationale for risk disclosure (e) Perceived barriers to risk disclosure (f) Importance of risk disclosure feedback elements 
Stage II:
 
 (a) Comprehension/recall of personal risk information (b) Psychological distress (mood, anxiety, and event-specific distress) (c) Satisfaction with feedback process (exploratory)

SECTION 1: Roles & Responsibilities - Contributorship

[name]. (ARF) – Principal Investigator

Affiliations: University of Michigan, Department of Psychiatry

Contact: [contact]

Roles & Responsibilities:

Design conception and initiation
Preparation of protocol and revisions
Managing correspondence with clinical trials office
Publication of study reports
Preparation of manuscripts
Recruitment and screening of patients
Data collection
Data entry, verification
Statistical Analyses
Regulatory and compliance management/adverse event reporting

[name]., ABPP-CN (BMH) – Co-Investigator

Affiliations: VA Ann Arbor Healthcare Systems, Mental Health Service

University of Michigan, Department of Psychiatry

Contact: [contact]

Roles & Responsibilities:

Design conception and initiation
Mentorship

J. [name]. (JSR) – Co-Investigator

Affiliations: University of Michigan, School of Public Health

Contact: [contact]

Roles & Responsibilities:

Design conception and initiation
Mentorship

[name], B.S. (ML) – Research Associate

Affiliations: University of Michigan, Department of Psychiatry

Contact: [contact]

Roles & Responsibilities:

Preparation of protocol and revisions
Managing correspondence with clinical trials office
Preparation of study reports
Preparation of manuscripts
Recruitment and screening of patients
Data collection
Data entry, verification
Statistical Analyses
Regulatory and compliance management/adverse event reporting

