1.1 Do African-American and White participants or co-participants differ in their interest in receiving certain types of DAT risk information? The study will evaluate group differences in participant and co-participant interest in and actual preference for feedback at five levels: (1) no information about AD risk, or risk information based on (2) standard clinical measures, (3) genetic information, (4) quantitative structural neuroimaging, (5) amyloid and tau PET. Exploratory analyses will assess whether group differences also exist based on clinical research diagnosis (normal vs. MCI), and whether participants and their co-participants agree.

1.2 Do African-American and White participants or co-participants differ in their perspectives on/rationale for certain types of DAT risk feedback? This study will assess whether African-American and White participants and co-participants identify different primary reasons for risk disclosure (i.e., basic curiosity, emotional reason, financial planning, medical planning, legal planning, social/family planning, or other). Exploratory analyses will assess whether group differences also exist based on clinical research diagnosis (normal vs. MCI), and whether participants and their co-participants agree.

1.3 Which characteristics predict risk disclosure interest in African-American vs. White participants and co-participants? This study will evaluate whether African-American and White participants and co-participants differ in their perceived threat of DAT, perceived benefits of risk disclosure, and perceived barriers to using risk information. We will also determine whether different factors (including personal demographic characteristics and the aforementioned perceived threat, benefits, and barriers) predict risk disclosure interest in different groups. Exploratory analyses will assess whether group differences also exist based on clinical research diagnosis (normal vs. MCI), and whether participants and their co-participants agree.

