Primary Outcome 1.3 (Patient characteristics that influence preferences): We will utilize a regression approach to determining patient characteristics and perspectives that shape level of interest. More specifically, we will create mixed linear models to quantify the fixed effects of four sets of variables (participant factors [demographics, baseline anxiety and depression, DAT knowledge], ADI Perceived threat of DAT, ADI Perceived benefits of this level of risk disclosure, ADI Perceived barriers to using this risk information), as well as the random effects attributable to the dyadic relationship. This approach will allow us to calculate the intra-class correlations representative of the effect of the dyadic relationship. Furthermore, given the likely effect of dyadic role ('patient' or informant) on perceived threat, perceived benefits, and perceived barriers, the interaction terms (e.g., role by threat, role by benefits, role by barriers) will also be included in the model. It is expected that the effect of the dyadic relationship will be significant; therefore, additional subgroup analyses examining predictors of risk disclosure interest in caregivers and patients *separately* will be conducted.

Primary Outcome 1.4 (Differences in importance of risk disclosure components): To analyze the Likert-style importance outcomes, either independent samples *t*-tests or Mann Whitney U tests will be used to compare mean interest level in African-American and White participants for each of the feedback components, again using a Bonferroni correction. Further exploratory correlation analyses will determine agreement between caregiver and informant interest in African-American and White subgroups, separately.

Secondary Outcome (Qualitative Information from Semi-Structured Interviews): In combination with the semi-structured interviews, we will therefore record and transcribe the narrative responses of patients and caregivers. After basic 'cleaning' of the data (removal of articles, non-content utterances, and additional identified 'stop' words), the text will be analyzed using R Statistical Software for most commonly used words or phrases by race. A Topic Modeling approach (akin to an exploratory factor analysis for text analysis) will be utilized to identify central themes (the 'factors') and associated terms or phrases (the 'items') by race.

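### Question 1.3 promises two comparisons by race, but the Stage I analysis section specifies neither

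*Combined protocol and SAP*

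**What the plan says.** Section 2.2, question 1.3, makes two commitments about African-American and White participants and co-participants. The first is to evaluate whether they "differ in their perceived threat of DAT, perceived benefits of risk disclosure, and perceived barriers to using risk information". The second is to "determine whether different factors (including personal demographic characteristics and the aforementioned perceived threat, benefits, and barriers) predict risk disclosure interest in different groups". The front summary table lists the same constructs as Stage I primary outcomes: (c) "Perceived personal threat of DAT", (d) "Perceived benefits of/rationale for risk disclosure", and (e) perceived barriers.

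Section 3.4.2.1 answers question 1.3 with a "regression approach to determining patient characteristics and perspectives that shape level of interest". This is a set of mixed linear models of interest with a random dyad effect. The fixed effects are participant factors (demographics, baseline anxiety and depression, DAT knowledge) and the ADI threat, benefits and barriers scores. On interactions it says that "the interaction terms (e.g., role by threat, role by benefits, role by barriers) will also be included in the model", and the reason given is the likely effect of dyadic role. It then adds "additional subgroup analyses examining predictors of risk disclosure interest in caregivers and patients", run separately for each role. The paragraph does not mention race.

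**The concern.** Both aims of question 1.3 are comparisons between races, and its analysis paragraph contains no such comparison. The paragraphs for 1.1, 1.2 and 1.4 and for the interview text all name the race comparison, so 1.3 is the exception.

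The gap falls on the question that motivates Stage I. Need 2 in Section 2.1 asks how and why racial groups differ in their preferences. Advancement 2 notes that perceived vulnerability seems lower among African-American people, and that nobody knows whether this explains a lower wish for disclosure. The first step towards an answer is to show whether the scores differ by race in this sample. If that is not specified, the choice of score, role and multiplicity rule is made after the data are in. The second aim, whether predictors work differently in the two groups, is a separate question, and the stated model has no term for it.

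**Working it through.** **Aims against analysis**

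| Aim in question 1.3 | What would answer it | What Section 3.4.2.1 gives |
|---|---|---|
| Scores differ by race | Each score as an outcome, compared by race | Scores as predictors of interest only |
| Predictors of interest differ by race | Race-by-predictor terms, or models split by race | Role-by-predictor terms; models split by role |

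The other paragraphs do not fill the gap. Outcome 1.1 compares interest by race, 1.2 compares the primary reason for disclosure, and 1.4 compares the importance of feedback components. Outcome 1.2 therefore covers the rationale part of primary outcome (d), but not the ADI benefits score.

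**Why race as a demographic covariate is not enough.** Write interest = a + b·race + c·threat + error. The coefficient b is a difference in interest, not in threat, and c is one slope shared by both races. With equal groups and equal predictor variance, true slopes of 0.6 and 0 give c of about (0.6 + 0)/2 = 0.3. Simulation gave 0.29 to 0.30.

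**Precision of the missing contrasts.** The plan states no power, alpha or sample size for 1.3, so there is no figure to reproduce. The nearby alpha for 1.1, .05/5 = .01, is correct.

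Inputs:
- 25 participants per race (Section 3.1.1), or 30 if the maximum of 60 splits equally.
- The co-participant split is not stated and is assumed to be the same.
- SD 1 is assumed.

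Half-width of the 95% CI for one score within one role = t(.975, 2n−2) × √(2/n):
- n = 25: 2.011 × 0.2828 = 0.569
- n = 30: 2.002 × 0.2582 = 0.517

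Difference detectable with 80% power (two-sample t, noncentral t distribution):

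| Alpha | n = 25 | n = 30 |
|---|---|---|
| .05 | 0.81 | 0.74 |
| .05/3 | 0.94 | 0.86 |
| .05/9 | 1.07 | 0.97 |
| .05/11 | 1.09 | 0.98 |

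Three contrasts apply if each score is computed once. Eleven (1 + 5 + 5) apply if benefits and barriers are scored at all five feedback levels. Nine (1 + 4 + 4) apply if the no-information level is left out.

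Roles combined, with n dyads per race and both members assumed to share race: SE = √(2(1 + ICC)/(2n)), multiplied by the same t. The half-width is 0.40 (n = 25) or 0.37 (n = 30) with ICC 0, and 0.49 or 0.45 with ICC 0.5.

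**Precision of race interactions.** Least-squares simulation with a race main effect, four predictors, three race interactions fitted together, and a slope of 0.6 in one race and 0 in the other:

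| n per race | Independent predictors: half-width, power | Predictor correlation 0.5 and five more covariates: half-width, power |
|---|---|---|
| 25 (one role) | 0.64, 46% | 0.84, 31% |
| 30 (one role) | 0.57, 55% | 0.73, 38% |
| 50 (pooled) | 0.42, 79% | 0.53, 61% |
| 60 (pooled) | 0.38, 88% | 0.47, 70% |

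For a slope difference of 0.3 within one role, power is about 11 to 18%. The pooled rows treat dyad members as independent. A separate pooled check used dyad ICC 0 or 0.5 and included the role interactions. It gave half-widths of 0.34 to 0.44 (independent predictors) and 0.43 to 0.55 (correlated), which are the better guide for the pooled model.

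**The case against.** The strongest reply is that race is not excluded. The word demographics plausibly covers it in a study built on two race groups, and the interaction list is introduced as examples, so race terms could be added. Both points are true, and it would be wrong to say that race is barred from the model. Neither supplies the analysis. A race main effect compares interest, not the scores. An open list justified by dyadic role does not prespecify a race term, and no interaction in a model of interest compares the scores.

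An adjusted race coefficient, read beside the unadjusted comparison in 1.1, would say something about whether the measured factors account for a difference in interest. That stands. It bears on the background question in Section 2.1, but not on either aim of question 1.3.

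The interviews include questions on the same Health Belief Model domains, and their text is analysed by race. This is a real by-race look at these constructs, but it is a secondary, qualitative outcome and does not compare the scores.

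Finally, the sample is small, and the precision figures rest on assumed SDs, correlations and slopes. They describe what the additions could deliver and do not measure harm from the omission. Small size is a reason to keep the interactions exploratory. It is not a reason to omit the contrasts, since 1.1 and 1.4 already compare the races at this sample size.

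**Conclusion.** The concern holds, with high confidence, and the wording should be fixed. It rests on the text alone: followed exactly, Section 3.4.2.1 gives no race contrast on threat, benefits or barriers, and no named term or split that shows whether predictors differ by race. Primary outcomes (c) and (e) have no quantitative race comparison, and (d) has one for rationale only.

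Under the stated assumptions, the added score contrasts would be informative only for large differences within a role: 0.86 to 0.94 SD with three contrasts, and up to 1.09 SD with eleven. The race interactions would be imprecise, with half-widths of 0.57 to 0.84 by role and 0.34 to 0.55 pooled, and cannot carry a confirmatory claim. Stage I is observational, so the gap affects what the study can report about race and not participant safety.

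**What to change.** 1. **Main change.** Add to Section 3.4.2.1 a race contrast with a 95% CI on each of the threat, benefits and barriers scores, by role, or with a dyad random effect if roles are combined. Apply a Bonferroni rule as in 1.1 and 1.4, and state that it governs claims of a difference while the 95% intervals are for estimation.
2. **Define the scores.** The model refers to "ADI Perceived benefits of this level of risk disclosure", so state whether benefits and barriers are scored once or per feedback level. Name the ADI items that form them, because the description of the ADI in Section 3.3.1 does not mention benefits of disclosure.
3. **Model.** Name race in the 1.3 model. Add race by threat, race by benefits and race by barriers as exploratory terms. Report race-specific slopes and their differences with 95% CIs, as estimates and not tests.
4. **Scope.** State that the other demographics stay as main effects because of the sample size, and narrow that part of question 1.3 to match.
5. **Timing.** Date the change. Stage I began enrolling on 10/22/19 and is still listed as recruiting in this version, so record whether any outcome data had been examined by race.

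The cost is wording only, with no new measures or participants. It adds three contrasts per role (nine or eleven if scored by level) and three exploratory terms in each of the pooled, patient and informant models, nine in all, or more if models are fitted by level. The price is more comparisons and wide intervals.

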1.4 Which components of feedback do African-American and White participants or co-participants see as most important? This study will evaluate whether African-American and White participants and co-participants differ in their perspectives on the relative importance of different component of risk disclosure (e.g., educational materials, visual aids, follow-up coordination with providers). Exploratory analyses will assess whether group differences also exist based on clinical research diagnosis (normal vs. MCI), and whether participants and their co-participants agree.

Objective 2: to develop person-centered, culturally-informed protocols for disclosure of different combinations of Alzheimer's dementia risk factors. Building on the results of Objective 1, we will produce protocols for communication of DAT risk, with attention to specific adaptations in style or content based on the above noted individual factors. In particular, protocols will specify (a) effective methods of communicating risk conferred by each data source, (b) information designed for patients versus informants, (c) psychoeducation needs, and (d) resource/support needs. Through piloting in Stage II, we will evaluate three outcomes in both participants (those receiving the feedback) and co-participants:

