HBM Components. We have developed the Anticipatory Dementia Inventory (ADI), a 50-item Likert-style measure of DAT-specific worry based on the HBM. Items relate to perceived vulnerability to DAT, perceived seriousness of a diagnosis, and expectations about ability to deal with a diagnosis, with responses ranging from strongly disagree to strongly agree. This measure has previously been validated for use with racially diverse older adults through the PI’s graduate work (paper in preparation).

Knowledge of AD/DAT. DAT knowledge will be measured through a multiple-choice quiz about DAT symptoms, course, causes, treatments, and risk factors. This quiz will be developed in Quarter 1 of the first funding year via monthly study-team meetings.

Risk Disclosure Interest and Preferences. In addition to the open-ended preference/rationale questions administered in the interview, we will utilize a questionnaire asking participants and co-participants to rate their level of interest in receiving feedback based on each risk factor (Table 3; e.g., “How interested are you in knowing about your/your family member’s risk for Alzheimer’s Dementia based on your genotype?”), on a continuous scale ranging from 1 (no interest) to 5 (very interested). Participants and co-participants will also use a checklist to state which information they would want to receive, selecting as many of the DAT risk information sources as desired (e.g., “Would you choose to receive feedback about your/your family member’s risk for DAT based on genotype? Yes or No?”)

Risk Disclosure Rationale. Participants will also be provided with a list of reasons for risk disclosure cited in prior literature and asked to rank the primary reason/purpose for risk disclosure.

Importance of Risk Disclosure Elements. Participants and co-participants will also complete a questionnaire asking them to rate the importance of different empirically supported elements of risk disclosure protocols cited in the published literature (e.g., How important do you think it is that educational materials are provided as part of your risk disclosure feedback?). Responses will be on a continuous scale from 1 (not at all important) to 5 (extremely important).

The order of questionnaires and interview questions will be counter-balanced to avoid potential reciprocal priming effects (e.g., discussing perceived vulnerability to DAT may influence feedback preferences).

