3.4.2.1 Stage I

Primary Outcome 1.1 (Differences in risk disclosure interest and preferences): To analyze the dichotomous yes/no interest outcomes, chi-squared analyses will be used to compare the proportion of African-American and White participants who endorse interest in receiving feedback at each level, for caregivers and patients separately. Given that there are five levels of risk disclosure feedback, five comparisons will be conducted; to account for the relatively small sample size, a conservative Bonferroni correction for multiple comparisons will be implemented ($\alpha = .05/5 = .01$). To analyze the Likert-style interest outcomes, either independent samples *t*-tests or Mann Whitney U tests will be used to compare mean interest level in African-American and White participants for each of the five risk disclosure levels, again using a Bonferroni correction. Further exploratory correlation analyses will determine agreement between caregiver and informant interest in African-American and White subgroups, separately.

Primary Outcome 1.2 (Differences in risk disclosure rationale): This study will assess whether African-American and White participants and co-participants identify different primary reasons for risk disclosure (i.e., basic curiosity, emotional reason, financial planning, medical planning, legal planning, social/family planning, or other), a Fisher's Exact test will be used, comparing frequency of reason endorsement. These analyses will be conducted for patients and informants separately; however, we will also explore agreement among dyad members.

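### Primary Outcome 1.4: Holm over the importance items would hold the same family-wise error as the planned Bonferroni correction and give up less power (minor improvement)

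*Combined protocol and SAP*

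**What the plan says.** Section 3.4.2.1 opens Primary Outcome 1.4 with "To analyze the Likert-style importance outcomes". It then plans t-tests or Mann-Whitney U tests to "compare mean interest level in African-American and White participants for each of the feedback components, again using a Bonferroni correction". It gives neither a number of components nor a per-test alpha.

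Outcome 1.1, in the same section, shows how the authors build the correction: "Given that there are five levels of risk disclosure feedback, five comparisons will be conducted", hence .05/5 = .01. The yes/no comparisons there are made "at each level, for caregivers and patients separately". Outcome 1.2 is also analysed separately for patients and informants. Outcome 1.4 does not mention role, although its objective in Section 2.2 asks "Which components of feedback do African-American and White participants or co-participants see as most important".

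The components are described in two places. Section 2.2 refers to the "relative importance of different component of risk disclosure (e.g., educational materials, visual aids, follow-up coordination with providers"), which is three examples. Section 3.3.1 describes a questionnaire asking respondents to "rate the importance of different empirically supported elements of risk disclosure protocols cited in the published literature", with one sample item and no item count. Table 2 lists nine steps of the Stage II disclosure session, but it is not presented as the Stage I importance questionnaire and does not supply m.

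**The concern.** Importance of feedback elements is a listed Stage I primary outcome. Section 2.2 also says "Building on the results of Objective 1, we will produce protocols for communication of DAT risk", so the importance results are meant to inform the Stage II material.

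The race comparison rests on 25 participants per group (Section 3.1.1), and every added item lowers the Bonferroni threshold. With single-step Bonferroni, each item must meet the strictest threshold whatever the other items show. Holm relaxes the threshold after each rejection at no cost in family-wise error. At stake is some avoidable loss of power to detect components that the two groups value differently. The validity of the tests is not in question.

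**Working it through.** **Inputs.** Family-wise alpha .05 and the divisor rule come from Outcome 1.1. The figure of 25 per race comes from Section 3.1.1; it is stated for participants and assumed here for co-participants. Not in the documents, and therefore assumed: m, the true differences, the correlation between items, and two-sided testing.

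**The plan's own figure.** For Outcome 1.1, .05/5 = .01, which reproduces exactly. No threshold is stated for Outcome 1.4, so there is none to reproduce.

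**Threshold for Outcome 1.4 under Bonferroni**, .05/m, and power per item from a two-sample t-test, 25 v 25, standardised difference 0.8:

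| m (assumed) | .05/m | Power |
|---|---|---|
| 3 | .0167 | .64 |
| 5 | .0100 | .56 |
| 8 | .00625 | .49 |
| 10 | .0050 | .46 |
| 15 | .0033 | .41 |
| 20 | .0025 | .37 |

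This column shows what Bonferroni costs as m grows. It does not measure harm from leaving m unstated.

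**Holm.** Order the p-values from smallest to largest. Compare the k-th with .05/(m − k + 1) and stop at the first that fails. For m = 10 the steps begin .05/10 = .0050, .05/9 = .0056, .05/8 = .00625, and reach .05/5 = .0100 at the sixth. Every step is at least .05/m, so any item that Bonferroni rejects Holm also rejects. Family-wise error is at most .05 under any dependence between items. Holm uses only the p-values, so it serves the t-test and the Mann-Whitney test alike.

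**Comparison by simulation.** 20,000 trials, 25 per race, m = 10, five true differences of 0.8 and five nulls, item correlation .3:

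| | Bonferroni | Holm |
|---|---|---|
| Average power per true difference | about .46 | about .50 |
| Any false rejection | about .023 | about .035 |

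Repeat runs agree within simulation error. As a check on the Bonferroni column, five true nulls at .005 each allow at most 5 × .005 = .025. Holm spends part of the error allowance that Bonferroni leaves unused, and stays below .05.

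**The case against.** The strongest reply is that nothing here is wrong. Bonferroni is valid for any m. Outcome 1.1 shows how the divisor is obtained, and m is the item count of a questionnaire completed before analysis. Stage I is an observational needs assessment, and no section makes Stage II content depend on a p-value crossing a threshold. On this view Holm is a matter of preference. Most of that stands, and it is why the point is minor. It does not show a disadvantage of Holm for these tests: the error guarantee is the same and the rejections include all of Bonferroni's. Two limits should be granted. The gain is small, and it vanishes when few items truly differ.

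A reader might infer more than the text supports:

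- **That .01 carries over from Outcome 1.1.** With m above 5 this would raise family-wise error, for example to 1 − .99^10 = 9.6% at m = 10 with independent items. But the .01 was derived from a count of five comparisons, and the correction in Outcome 1.4 attaches to its own set of tests. The natural reading is .05/m, under which family-wise error is at most 5% for any m.
- **That the threshold is left to discretion at analysis.** Nothing suggests that items are chosen after results are seen.
- **That interest, not importance, is analysed.** The heading and opening clause of Outcome 1.4 both say importance, and Section 3.3.1 defines a 1-to-5 importance scale. The phrase is a wording slip.

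**Conclusion.** This is a minor improvement, not an error. The planned correction controls family-wise error. Holm over the same items controls it equally and can only add rejections. Under the assumptions shown (m = 10, five true differences of 0.8, item correlation .3, 25 per race), average power rises by about .03 to .04, from about .46 to about .50. The chance of any false rejection remains below .05. The size of the gain depends on those assumptions; the two general properties do not. The missing count is a detail to supply when the sentence is revised, and no inflated error rate follows from its absence. The point asks for no change to Outcome 1.1.

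**What to change.** In Primary Outcome 1.4, replace the Bonferroni correction with Holm's procedure over the m importance items (first step .05/m). Apply it within each role, in line with the separate analyses in Outcomes 1.1 and 1.2, and state m from the questionnaire. While editing, change the reference to interest level to importance rating.

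The cost is one or two sentences. Data collection, sample size and the choice of test are unaffected. The only burden is reporting: p-values must be ordered, or given as Holm-adjusted values, because no single threshold applies to every item.

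### Question 1.4 asks which feedback components matter most and about their relative importance, but the plan tests raw ratings by race one component at a time and never compares components

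*Combined protocol and SAP*

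**What the plan says.** **Question.** Section 2.2, question 1.4, asks "Which components of feedback do African-American and White participants or co-participants see as most important", and whether the races "differ in their perspectives on the relative importance of different component of risk disclosure".

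**Data.** Section 3.3.1 (Importance of Risk Disclosure Elements) collects a separate 1-to-5 rating of each element. No ranking or forced choice among elements is requested. A ranking is requested only for the rationale outcome, where people are "asked to rank the primary reason/purpose for risk disclosure".

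**Analysis.** Section 3.4.2.1, Primary Outcome 1.4, uses a t-test or Mann-Whitney test to "compare mean interest level in African-American and White participants for each of the feedback components", with a Bonferroni correction. The only other analysis given there is on dyads: "Further exploratory correlation analyses will determine agreement between caregiver and informant interest in African-American and White subgroups, separately". Section 2.2 adds exploratory comparisons by diagnosis. The data screening in Section 3.4.2 covers missing data, ranges, outliers, distribution shape and session modality, but not a person's overall rating level.

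**The concern.** Both halves of question 1.4 compare components with each other: which come out on top, and whether their standing relative to one another differs by race. The planned tests make a different comparison, of one component's mean in one race against the same component's mean in the other. Three consequences follow.

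- No ordering of components is specified, so *most important* has no planned answer.
- If one group rates everything higher, several components can differ by race although both groups order them identically.
- If the groups value components differently around the same average, each single-item difference may be too small to pass the corrected threshold, although the overall pattern is clear.

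Section 2.1 (Advancement 1) says the results will describe the distinct disclosure needs of the two races. A statement of that kind needs to say whether it concerns overall level or relative importance. The word *interest* in the 1.4 sentence belongs to Outcome 1.1; the outcome here is importance.

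**Working it through.** **1. The plan's own figure.** For Outcome 1.1, "a conservative Bonferroni correction for multiple comparisons will be implemented" with 0.05/5 = 0.01, which reproduces. Outcome 1.4 refers back to this but states neither the number of components nor a divisor.

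**2. What the planned test estimates.** Write the mean rating of component k in race g as μ + L(g) + c(k) + r(g,k), with the r terms summing to zero over components within each race. The planned contrast for component k is [L(1) − L(0)] + [r(1,k) − r(0,k)]. The term c(k), which drives the ordering, cancels. The level difference L is mixed into every item. *Most important* concerns c(k) + r(g,k); *relative importance* by race concerns r(1,k) − r(0,k). Neither is isolated.

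**3. Inputs.** 25 per race (Section 3.1.1). Assumed, because the documents do not state them: 10 components, SD 1, between-item correlation 0.5, two-sided tests. Corrected alpha = 0.05/10 = 0.005; critical t on 48 df = 2.94; standard error of a raw item difference = √(2/25) = 0.283. An observed difference must therefore exceed 2.94 × 0.283 = 0.83 SD to be flagged.

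**4. Relative importance differs, level does not.** Let the race difference be +0.3 SD and −0.3 SD on alternate components.
- Planned tests, any component flagged: about 26% of simulated studies.
- Race-by-component test: about 94%. Analytic check: within-person variance = 1 − 0.5 = 0.5; noncentrality = (25/2) × 10 × 0.3² / 0.5 = 22.5; on 9 and 432 df at 0.05 the power is 93%.
- At 0.2 SD: about 12% against 55%.
- With ratings rounded and clipped to 1–5, at 0.3 SD: about 23% against 85%.

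**5. Level differs, relative importance does not.** One group rates every component higher by a constant.

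| Shift (SD) | Noncentrality, shift/0.283 | At least one component flagged | Mean number flagged |
|---|---|---|---|
| 0.3 | 1.06 | 20% | 0.4 |
| 0.5 | 1.77 | 50% | 1.4 |
| 0.7 | 2.47 | 79% | 3.4 |

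The last column agrees with 10 × single-item power: 10 × 0.037 = 0.37, 10 × 0.133 = 1.33 and 10 × 0.332 = 3.32. After centring each person's ratings on that person's own mean, 4% to 6% of studies flag any component.

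A separate simulation with correlation 0.4 and ratings rounded to 1–5 gave 14% at a 0.25-point shift and 54% at 0.5. Mann-Whitney gave 12% and 49%, so the plan's alternative test does not help. With no shift, both tests flagged about 4%.

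**6. The ceiling.** With component means running from 3.0 to 4.8 in one group, the other group shifted up, and ratings clipped at 5, person-centred tests flag at least one component in about 12%, 18% and 46% of studies at shifts of 0.5, 0.7 and 1.0. The ceiling compresses the top-rated items and creates an apparent race-by-component difference. Centring lowers the false-difference rate but does not remove it.

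**The case against.** The strongest defence is that the outcome is listed simply as the importance of feedback elements, and its analysis heading speaks of differences in importance. An item-by-item race comparison answers that directly and holds its error rate when the groups do not differ. Group means will be computed anyway and can be sorted by eye. The interviews are also analysed by race.

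Much of this stands. The per-item tests are valid tests of absolute importance and should be kept. But Section 2.2 asks the relative question in so many words. Sorting means informally gives no intervals and is not planned, and the dyad, diagnosis and interview analyses do not order the rated components.

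Two stronger readings should be resisted. A reader might infer that the plan will report differences in scale use as differing needs. Nothing in the documents shows that the races use the scale differently, and a uniform shift could be a true difference in how much importance one group attaches to feedback support overall. The 20%, 50% and 79% are conditional on an assumed shift, not expected error rates. A reader might also infer that these item tests decide what Stage II emphasises for whom. Objective 1 informs the protocols in general, but the personalisation rules in Section 3.3.2 use demographics, home location, diagnosis, risk level and the indicators requested, not these tests.

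**Conclusion.** The mismatch between question and analysis is established from the text alone. As planned, Outcome 1.4 gives no ordering of components, cannot tell a difference in overall level from one in relative importance, and is weak for the latter: about 26% against 94% for a 0.3 SD alternating pattern, or 23% against 85% on a bounded 1–5 scale. These sizes rest on assumed values for the number of components, SD, correlation and pattern of differences. Part of the gain comes from testing the pattern jointly and part from removing between-person variance. The planned tests are not invalid; they answer a different question. The change is worth making because a stated primary question is otherwise left unanswered. Safety and the Stage II outcomes are unaffected.

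**What to change.** In Section 3.4.2.1, Primary Outcome 1.4:

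1. For each role (participant, co-participant), fit one mixed model of importance on component, race and component × race, with a random person intercept.
2. Report the ordering of components with confidence intervals, overall and by race. This answers *most important*.
3. Use the interaction as the test of relative importance, with race contrasts on person-centred ratings to show where any difference lies. Those contrasts, if corrected item by item, have less power than the joint test.
4. Report the race main effect separately as a difference in overall level, without calling it artefact.
5. Keep the per-item raw comparisons as absolute-importance results, and state the number of components and the Bonferroni divisor.
6. Because the scale stops at 5, add a sensitivity analysis on within-person ranks or with an ordinal model.
7. Replace *interest* with *importance*.

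The cost is SAP wording and a little more analysis. No new data are needed: the protocol already provides for these ratings, and mixed models are already planned for Outcome 1.3. If ratings have been examined by race before the change is made, the amendment should say so.
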